Participants will be treated with nemiralisib or placebo in addition to SoC. The study is designed to assess the dose response, efficacy, safety, and pharmacokinetics of nemiralisib across a range of doses (up to 750 mcg) compared with placebo for 12 weeks, with an additional 12-week post-treatment follow-up period. The range of doses to be evaluated in this study should be sufficient to enable full characterization of the dose response curve of nemiralisib, with respect to the primary endpoint (change from baseline in Clinic Visit trough forced expiratory volume in one second [FEV₁] measured post-bronchodilator at Day 84). This study is also designed to estimate the rate reduction of re-exacerbations on a selected dose of nemiralisib compared with placebo.

The information obtained from study 200879 will be used to select the optimally effective and safe dose of nemiralisib for further COPD studies. In addition, this study will evaluate and confirm the pharmacokinetic (PK) profile of nemiralisib within a subset of the patient population.

Objectives and Endpoints:

Objective	Endpoint
Primary	

To characterize the dose response of nemiralisib administered in addition to SoC compared with placebo and SoC in participants diagnosed with an acute moderate or severe exacerbation of COPD
	
Change from baseline in Clinic Visit trough FEV₁ at Day 84 measured post-bronchodilator
 
Baseline is defined as the post-bronchodilator FEV₁ measured prior to the first dose of double-blind study treatment on Day 1.

Secondary	

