1. The start of the SoC for the index exacerbation is defined as the start of either oral/systemic corticosteroids[s] or antibiotic[s] whichever is earliest and is expected to start shortly after diagnosis, though it may already have been started before formal diagnosis of COPD exacerbation. If SoC is started >48 hours prior to diagnosis, the participant is not eligible to participate, but may be re-screened in the future as described in the main protocol.
2. All Screening/baseline assessments should be completed within 48hrs of start of SoC.

12-Week Double-Blind Treatment Period: Once-daily study treatment administration will start on Day 1 (Visit 2).

At the end of the Screening Period (-2 to -1/0 days), participants who meet all of the Inclusion Criteria and none of the Exclusion Criteria will complete Visit 2 (Randomization Visit/Day 1). If a participant meets all of the eligibility criteria, it is possible for him/her to complete the Screening Visit and the Randomization Visit on the same day (e.g., outpatient participant who presents with an acute moderate exacerbation of COPD).

At this visit, participants will be randomized to receive one of the doses of nemoralisib QD or placebo QD in addition to SoC for 12 weeks.

Randomization and the first dose of the double-blind study treatment administration should take place in the morning, as soon as possible following determination of eligibility and completion of the baseline PRO measures, including the EXACT-PRO questionnaire for the day of randomization, and FEV₁ measurement and no later than 48hrs after the start of SoC.

Note: In the event that completion of the assessments/procedures at Visit 2 (or in cases where Visit 1 and Visit 2 are conducted on the same day) extends past noon, the first dose of the double-blind study treatment administration may occur up until 3:00 pm on Day 1. After Day 1, dosing should take place in the morning each day through the end of the 12-Week Double-Blind Treatment Period.

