Spirometry assessments performed during a moderate or severe COPD exacerbation.		If a participant is unable to achieve the required standard of spirometry per Section 9.1.1 during a moderate or severe COPD exacerbation, they will be permitted to continue in the study. The protocol has anticipated that this is likely for hospitalised participants and therefore spirometry will be repeated at discharge for a secondary endpoint.
Feeling faint, or experiencing mild pain, bruising, irritation or redness at the injection site during the blood withdrawals In rare cases, an infection where the needle entered the skin		The medically qualified site staff conducting the phlebotomy will follow standard medical practice to minimize these risks
Skin irritation from the ECG electrodes placed on the participant's chest		The medically qualified site staff conducting the ECG measurement will follow standard medical practice for performing the ECG
Risk of radiation from a chest X-ray		As specified in the protocol: 
 • A chest X-ray (CT scan), for purposes of determining participant eligibility, will be performed only at the Screening (Visit 1).

Potential Risk of Clinical Significance	Summary of Data/Rationale for Risk	Mitigation Strategy
		

• A chest X-ray (conducted within 48 hours of diagnosis) for confirmation of a suspected case of pneumonia, is encouraged rather than required

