4. OBJECTIVES AND ENDPOINTS

Objectives	Endpoints

Primary
 
 To characterize the dose response of nemiralisib administered in addition to SoC compared with placebo and SoC in participants diagnosed with an acute moderate or severe exacerbation of COPD 	
 Change from baseline in Clinic Visit trough forced expiratory volume in one second (FEV₁) at Day 84 measured post-bronchodilator Baseline is defined as the post-bronchodilator FEV₁ measured prior to the first dose of double-blind study treatment on Day 1.

Secondary
 
 To characterize the dose response and efficacy of nemiralisib administered in addition to SoC compared with placebo and SoC in participants diagnosed with an acute moderate or severe exacerbation of COPD 	
 Rate of moderate and severe exacerbations over the 12-Week Treatment Period Time to next moderate/severe exacerbation following index exacerbation Change from baseline in Clinic Visit trough FEV₁ measured pre and post-bronchodilator at Days 14, 28, 56, and 84 (Day 84: post-bronchodilator is the primary endpoint; pre-bronchodilator is a secondary endpoint) and at hospital discharge (only for participants who are hospitalized for the index

Objectives	Endpoints

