9.1.1. Spirometry Testing

Spirometry assessments will be obtained using spirometry equipment that meets or exceeds the minimal performance recommendations of the ATS [Miller, 2005]. All participating sites will use standardized spirometry equipment provided by an external vendor contracted by GSK.

All participants will perform lung function maneuvers to assess FEV₁, and FVC at each study visit. For each testing session, at least 3 valid spirometry efforts should be attempted (with no more than 8) using the ATS guidelines [Miller, 2005]. The highest FEV₁ from the valid forced expiratory curves for each testing session will be used.

Protocol-specified spirometry will be performed in the morning (i.e., initiated between 6:00AM and 12:00PM) during visits when clinic FEV₁ is performed as shown in the SoA (Section 2). In addition, protocol-specified clinic FEV₁ must be completed in accordance with the lifestyle restrictions as defined in Section 6.3.1- Section 6.3.5.

During Visits 2 through Visit 6, spirometry will be performed prior to administering double-blind study medication at two time points: pre-bronchodilator (albuterol [salbutamol]) and post-bronchodilator. Post-bronchodilator FEV₁ will be conducted approximately 10 to 30 minutes after the participant-administers 4 inhalations of albuterol (salbutamol) via MDI (i.e., total of 400 mcg) using a spacer/valved-holding chamber or via one nebulized treatment. It is anticipated that participants who are enrolled into the study will receive albuterol as part of the routine treatment of AECOPD during visit 2. In this instance, spirometry should be scheduled to coincide with this treatment to allow post-bronchodilator recordings to be measured. During Visits 6-9, spirometry will be performed prior to administering maintenance COPD medication(s) at two time points: pre-bronchodilator (albuterol [salbutamol]) and post-bronchodilator (as defined above).

Rescue albuterol [salbutamol] should be withheld for 4hrs prior to spirometry measurements, where possible. Usual daily COPD medications should be withheld on the morning of spirometry assessments, where possible.

Baseline Clinic Visit FEV₁ is defined as the post-bronchodilator FEV₁ performed at Visit 2.

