Simulations of change from baseline FEV₁ data have been performed to evaluate the probability of achieving end of study success criteria given the estimated sample size for each dose for various assumed scenarios. Three scenarios were considered, each based on different assumptions of the change from baseline FEV₁ for each of the treatment arms. The scenarios are described in [Table 3](#). The estimate of the dose response profile were obtained from fitting a 3-parameter Emax dose response model to simulated change from baseline FEV₁ data for the expected end of study sample size given these assumed true scenarios. A 3 parameter model was used rather than a 4 parameter model to improve the model convergence under simulation conditions. For the purpose of simulations, a frequentist analysis technique was used which should provide analogous results to fitting non-informative prior distributions for all modelling parameters using a Bayesian framework. A baseline and a single post dose observation were simulated for each subject using the bivariate normal distribution, assuming the between participant standard deviation of 300 mL for both time points, and a correlation of 0.7 between them. The average baseline was considered to be 1.383 L. These values were obtained from the PoC Study PII1116678 (a randomised, double-blind, placebo-controlled, parallel-group, study to evaluate the efficacy and safety of GSK2269557 administered in addition to standard of care in 126 participants diagnosed with an acute exacerbation of COPD). For each simulation, the appropriate number of participants was simulated using the expected sample size completing Day 84 as described in [Table 2](#). For each scenario, 5,000 iterations of simulations were run with each simulation analyzed using proc nlmixed in SAS.

Table 3 Change from Baseline in FEV₁ Assumptions for Three Assumed Scenarios

Dose	Scenario 1	Scenario 2	Scenario 3
Placebo	-20 mL	-20 mL	-20 mL
12.5 mcg	-15 mL	-15 mL	-20 mL
50 mcg	-15 mL	-10 mL	-20 mL
100 mcg	20 mL	10 mL	-15 mL
250 mcg	50 mL	30 mL	-10 mL
500 mcg	80 mL	40 mL	0 mL
750 mcg	80 mL	50 mL	0 mL

Table 4 shows the probability of achieving various criteria under the three assumed scenarios:

Table 4 Probability of Achieving Various Criteria under the Three Assumed Scenarios

Criteria	Scenario 1	Scenario 2	Scenario 3
Observed lowest dose difference from placebo <25 mL ¹	53%	62%	88%

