10.2. Populations for Analyses

For purposes of analysis, the following populations are defined:

Population	Description
All Participants Enrolled (APE) Population	All participants who are screened for eligibility
Modified Intent-to-Treat (MITT)	All randomized participants who receive at least one dose of study treatment. Participants will be analyzed according to the treatment that they were randomised to. The MITT Population will be used for all efficacy summaries.
Per-Protocol (PP) Population	The PP population is comprised of the MITT population, excluding any participants with an important protocol deviation. The PP population will be used to present sensitivity analyses for the primary and key secondary efficacy endpoints.
Safety Population	All randomized participants who receive at least one dose of study treatment. Participants will be analyzed according to the treatment they actually received. The Safety Population will be used for all safety summaries.
Pharmacokinetic (PK) Population	All participants in the MITT Population for whom a pharmacokinetic sample was obtained and analyzed. The PK population will be used for all PK summaries.

In the event one or more investigators are withdrawn from the trial due to concerns over protocol deviations, then a further population will be defined, which will consist of all participants in the MITT population excluding participants from those investigators. This population will be used to perform additional sensitivity analysis for the primary and key secondary efficacy endpoints.

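### The primary endpoint depends on a Day 1 FEV1 that the protocol expects some, mainly hospitalised, participants may not perform to standard, and neither the printed primary model nor the sample size allows for a missing baseline

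*Protocol*

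**What the plan says.** The Synopsis and Section 4 give one source for the baseline of the primary endpoint: "Baseline is defined as the post-bronchodilator FEV₁ measured prior to the first dose of double-blind study treatment on Day 1". Section 9.1.1 repeats it: "Baseline Clinic Visit FEV₁ is defined as the post-bronchodilator FEV₁ performed at Visit 2". No substitute is named. The measurement falls in the acute phase, because the Synopsis requires that "All Screening/baseline assessments should be completed within 48hrs of start of SoC". Section 9.1.1 takes the highest FEV1 from the valid curves of a session.

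The study-procedures part of the risk table in Section 3.3.1 deals with participants who cannot reach the spirometry standard during a moderate or severe exacerbation: "they will be permitted to continue in the study". It then states: "The protocol has anticipated that this is likely for hospitalised participants and therefore spirometry will be repeated at discharge for a secondary endpoint". Section 4 accordingly lists FEV1 at discharge, and change from discharge, among the secondary endpoints.

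The primary model in Section 10.3.1 is an Emax curve whose response is change from baseline FEV1. Section 10.2 says of the analysis population: "The MITT Population will be used for all efficacy summaries". Table 2 gives the numbers expected to complete dosing and provide a Day 84 FEV1. Section 10.1.1 simulates exactly those numbers: "A baseline and a single post dose observation were simulated for each subject using the bivariate normal distribution".

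**The concern.** Section 3.3.1 foresees a problem with the Day 1 measurement, and its remedy reaches only a secondary endpoint. For the primary endpoint the provisions do not fit together. The participant is retained and belongs to the MITT population, and may attend Day 84 and blow a valid FEV1. With no valid Day 1 curve, however, there is no response value to enter in the printed model.

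Two things are at stake. Valid Day 84 data would be discarded, on top of the 20% withdrawal already allowed for. The discarded data would also come mainly from hospitalised participants, so the primary dose response would lean towards participants with milder exacerbations, although the objective covers moderate and severe ones. Section 10.3.5 uses the same model at the interim analyses that may change allocation or add the 25 mcg arm, so the gap carries over to those decisions.

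**Working it through.** **Inputs from the protocol.** Randomised 340 (placebo), 114 (each of five doses) and 340 (750 mcg); withdrawal 20%; SD 300 mL at both time points; correlation 0.7 (Sections 10.1 and 10.1.1).

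**Reproducing Table 2.** 340 × 0.8 = 272; 114 × 0.8 = 91.2, printed as 91; 2 × 272 + 5 × 91 = 999; 1,000 / 0.8 = 1,250. Withdrawal alone explains the table, so nothing is set aside for a missing baseline.

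**Assumption.** Neither the hospitalised share nor the share of those with no valid Day 1 curve is stated. The loss among completers is the product of the two. For illustration, 20% × 25% = 5% and 50% × 40% = 20%. Completers with an evaluable change would then be 999 × 0.95 = 949 or 999 × 0.80 = 799.

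**Variances per participant.**
- Change score: 2 × 300² × (1 − 0.7) = 54,000
- Day 84 adjusted for baseline: 300² × (1 − 0.7²) = 45,900
- Day 84 alone: 300² = 90,000

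**Standard error of 750 mcg minus placebo.** Let n be the number per arm with both values and k the number with Day 84 only, so that n + k = 272.
- Change score, complete cases: √(2 × 54,000 / n)
- Baseline-adjusted, complete cases: √(2 × 45,900 / n)
- Joint model: √(2 / (n/45,900 + k/90,000))

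| Loss | n | k | Change score | Adjusted, complete cases | Joint model |
|---|---|---|---|---|---|
| 0% | 272 | 0 | 19.9 mL | 18.4 mL | 18.4 mL |
| 5% | 258.4 | 13.6 | 20.4 mL | 18.8 mL | 18.6 mL |
| 20% | 217.6 | 54.4 | 22.3 mL | 20.5 mL | 19.3 mL |

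The change-score standard error rises by a factor √(1/0.95) = 1.026 or √(1/0.80) = 1.118, that is by 2.6% or 11.8%. At 20% loss, the step from 22.3 to 20.5 mL comes from baseline adjustment and the step from 20.5 to 19.3 mL from the recovered Day 84 values.

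**Effect on success.** Take the 20 mL difference of Scenario 3 and a one-sided 0.10 threshold for the pairwise contrast. The probability is Φ(20/19.93 − 1.2816) = 39% with no loss and Φ(20/22.28 − 1.2816) = 35% at 20% loss.

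These are pairwise approximations that treat the baseline mean and slope as known. They do not reproduce the Emax fit behind Table 4 and do not show Table 4 to be wrong.

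**The case against.** Several points stand against a stronger reading.

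- A reader might infer that hospitalised participants as a group often have no primary outcome. The text does not say that. Section 9.1.1 asks for at least three valid efforts to be attempted and uses the best valid one. Someone with one or two valid curves can miss the standard and still have a usable value. Only those with no valid curve lose the baseline, and their number is not stated.
- Sections 5.1, 7.1 and 9 and the Synopsis place first dosing after the baseline FEV1, so the protocol plainly expects a Day 1 value. This narrows the problem, but it is not reconciled with the retention rule in Section 3.3.1.
- A reader might equate the severe stratum with hospitalised participants. Section 12.9.2 also counts emergency-room visits as severe, so a failure rate among hospitalised participants cannot be applied to the whole stratum.
- A reader might infer biased treatment comparisons. Day 1 spirometry precedes dosing and randomisation is stratified by severity, so a missing baseline does not by itself distort differences between arms.
- Section 10.3.4 plans a longitudinal analysis of trough FEV1 at all measured times. That helps dose selection but does not replace the primary analysis.
- The Reporting and Analysis Plan, not shown here, may add a rule, and a Bayesian fit can treat a missing baseline as unknown. It can do so only if baseline is itself modelled, which the printed form does not do. The baseline definition, response variable and evaluable numbers are all fixed in the protocol.

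**Conclusion.** The point holds in a limited form. Any participant with no valid Day 1 curve has no primary outcome under the printed model, whatever is measured at Day 84, and the sample size makes no allowance for this. The size is unknown. Under the illustrative 5% to 20% loss, precision for 750 mcg versus placebo worsens by about 3% to 12%, and the effect on the chance of success is modest. The lasting harm is that hospitalised participants count for less in the primary answer than the objective implies. That would shift the result only if their response to treatment differs.

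The conclusion rests on the protocol's SD and correlation and on an assumed loss that is equal across arms. The change is worth making because it costs little and improves precision even with no missing baselines (19.9 to 18.4 mL).

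**What to change.** 1. In Section 10.3.1, fit the Emax dose-response model jointly to Day 1 and Day 84 post-bronchodilator FEV1, with a baseline mean common to all arms, preferably one per severity stratum. MITT participants with a valid Day 84 value but no valid Day 1 value then contribute, and baseline is adjusted for. With a common baseline mean, the difference in Day 84 means equals the difference in mean change, so the placebo-corrected quantity is unchanged. Section 10.1.1 already simulates this bivariate normal structure.
2. State that the discharge FEV1 is not used as baseline, because it is measured after dosing has begun.
3. Base inference on placebo-corrected differences. Report within-arm mean changes alongside a complete-case sensitivity analysis: if the missing baselines tend to be the lowest, the joint model overstates baseline and understates mean change in every arm.
4. State at Table 2 that it counts participants with a Day 84 FEV1, not those with an evaluable change from baseline.
5. Reconcile the retention rule in Section 3.3.1 with the statements in the Synopsis and Sections 5.1, 7.1 and 9 that place randomisation or first dosing after the FEV1 measurement.

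The cost is protocol wording and a slightly larger model, with no new visits, data or participants. The downside is a missing-at-random assumption, which matters mainly for the within-arm means.

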3.3.2. Benefit Assessment

The outcomes of this study will provide information that may produce advances in knowledge of treatment of COPD, particularly the unmet need for more effective treatment of acute moderate and severe exacerbations of COPD, leading to a potential health benefit in the future for patients in this target population. The outcomes of this study will also help to determine the lowest effective and safe dose(s) of nemiralisib to be evaluated in future studies of nemiralisib.

3.3.3. Overall Benefit:Risk Conclusion

The benefit:risk for nemiralisib is supportive of further clinical evaluation in Phase IIb development. Study 200879 is designed to determine whether nemiralisib could have the potential as a new therapeutic option for the treatment of acute moderate and severe exacerbations of COPD. The data from this study will also provide information that may contribute to advances in the knowledge of acute exacerbations of COPD and may lead to a potential future health benefit in the clinical management of patients in this target population.

4. OBJECTIVES AND ENDPOINTS

Objectives	Endpoints

Primary
 
 To characterize the dose response of nemiralisib administered in addition to SoC compared with placebo and SoC in participants diagnosed with an acute moderate or severe exacerbation of COPD 	
 Change from baseline in Clinic Visit trough forced expiratory volume in one second (FEV₁) at Day 84 measured post-bronchodilator Baseline is defined as the post-bronchodilator FEV₁ measured prior to the first dose of double-blind study treatment on Day 1.

Secondary
 
 To characterize the dose response and efficacy of nemiralisib administered in addition to SoC compared with placebo and SoC in participants diagnosed with an acute moderate or severe exacerbation of COPD 	
 Rate of moderate and severe exacerbations over the 12-Week Treatment Period Time to next moderate/severe exacerbation following index exacerbation Change from baseline in Clinic Visit trough FEV₁ measured pre and post-bronchodilator at Days 14, 28, 56, and 84 (Day 84: post-bronchodilator is the primary endpoint; pre-bronchodilator is a secondary endpoint) and at hospital discharge (only for participants who are hospitalized for the index

Objectives	Endpoints

 To evaluate the treatment effect of nemiralisib in addition to SoC compared with placebo and SoC on symptoms indicative of an exacerbation and on health status using Patient-Reported Outcomes (PROs) in participants diagnosed with an acute moderate or severe exacerbation of COPD To evaluate the usage of rescue medication in participants diagnosed with an acute moderate or severe exacerbation of COPD 	
exacerbation)
 
 Change from hospital discharge in clinic visit trough FEV₁ measured pre- and post-bronchodilator at Days, 14, 28, 56, and 84 (in participants hospitalized for index exacerbation only) 
EXAcerbations of Chronic Pulmonary Disease Tool (EXACT-PRO)
 
 Proportion of participants achieving the EXACT definition of recovery from the index exacerbation by Days 14, 28, 56, and 84 Time to recovery from index exacerbation Severity of subsequent HCRU-defined exacerbation(s) defined by EXACT 
COPD Assessment Test (CAT)
 
 Proportion of responders using the CAT at Treatment Days 28, 56, and 84, and following EXACT defined recovery from the index exacerbation Change from baseline (Day 1) in CAT total score at Days 28, 56, and 84 and following EXACT defined recovery from the index exacerbation 
St. George's Respiratory Questionnaire (SGRQ) Total Score
 
 Proportion of responders on the SGRQ total score as measured by the SGRQ for COPD Patients (SGRQ-C) at Days 28, 56, and 84 Change from baseline (Day 1) in SGRQ total score at Days 28, 56, and 84 Rescue medication use (occasions/day), averaged over each week of treatment and over the 84-day treatment period The percentage of rescue-free days (24-

Objectives	Endpoints

 • To evaluate the population pharmacokinetics of nemiralisib in participants diagnosed with an acute moderate or severe exacerbation of COPD • To assess the safety and tolerability of nemiralisib and placebo in participants diagnosed with an acute moderate or severe exacerbation of COPD 	
hour periods) during each week of treatment and over the 84-day treatment period
 
 • Plasma nemiralisib concentrations and derived PK parameters (e.g., area under the curve [AUC (0-24) and AUC(0-t)], maximum concentration [C_{max}], time at maximum concentration [T_{max}], C_{trough}) as appropriate will be collected in a subset of randomized participants (approximately 300) at selected sites as follows: trough (pre-dose) for the study treatment and post-dose for the study treatment from 0-1 hour and >1 to 6 hours on Days 14 and 28 of the 12-Week Treatment Period • Incidence of adverse events (AEs; including serious AEs and AE of Special Interest [AESI]) • Vital signs (pulse rate, systolic and diastolic blood pressure) (measured at each clinic visit up through Visit 7 [Day 112] or Early Withdrawal Visit) • 12-lead electrocardiogram (ECG) assessments (performed at clinic Visits 1 [Screening], 3 [Day 14], 6 [Day 84], and 7 [Day 112] or Early Withdrawal Visit) • Clinical laboratory tests (hematology and chemistry; performed at each clinic visit up through Visit 7 [Day 112] or Early Withdrawal Visit) • Incidence of COPD exacerbations

Exploratory – 12-Week Treatment Period
 
 • To further characterize the dose response, and efficacy, of nemiralisib administered in addition to SoC compared with placebo and SoC in participants diagnosed with an acute moderate or severe exacerbation of COPD 	
 • Rate of mild exacerbations over the 12-Week Treatment Period • Rate of all exacerbations (mild, moderate and severe combined) over the 12-Week Treatment Period • Time to next exacerbation (mild, moderate

Objectives	Endpoints

 • To evaluate the treatment effect of nemiralisib in addition to SoC compared with placebo and SoC on symptom stability following an exacerbation using Patient-Reported Outcomes in participants diagnosed with an acute moderate or severe exacerbation of COPD • To explore the PK/PD relationship for nemiralisib • To evaluate the treatment effect of nemiralisib in addition to SoC compared with placebo and SoC on HCRU in participants who experience a severe exacerbation of COPD • To evaluate the compliance with study treatment • To evaluate inflammatory markers in blood in relation to acute exacerbation of COPD • To evaluate inflammatory and infective markers in sputum in relation to acute 	
and severe combined)
 
 • Stability of symptoms post recovery measured using E-RS:COPD (Evaluating Respiratory Symptoms in COPD) and subscales from Randomization (Visit 2) to Day 84 (Visit 6) • Relationship between drug exposure and Pharmacodynamic responses (e.g. efficacy, heart rate, clinical laboratory analytes and blood biomarkers) in the PK subset of participants (approximately 300) at selected sites. • Measures of HCRU related to severe exacerbations (e.g., hospitalizations, length of hospital stay, re-hospitalization within 30 days, number of Emergency Room [ER] visits, etc.) • Number of actuations of the double-blind study treatment as measured by the clip-on Propeller Sensor (for countries where the Propeller Sensor for ELLIPTA is available) • Blood samples collected at Screening through Visit 7 (as part of the clinical laboratory blood samples) for analysis of blood eosinophil counts and inflammatory mediators • Blood samples for analysis of inflammatory biomarkers (including but not limited to: high sensitivity C-reactive protein [hs-CRP], chemokine interferon-γ inducible protein 10 kDa (CXCL10)], and procalcitonin) collected at Visit 1 (Screening) • Spontaneous sputum sample for analysis of

Objectives	Endpoints
exacerbation of COPD	inflammatory and infective markers collected at Screening/Day 1 (pre-dose) and Day 56 in participants who are willing and able to provide a sample

Exploratory – Follow-Up Period
 
To evaluate the potential post-treatment impact of double-blind study treatment during the 12-Week Post-Treatment Follow-Up Period
	
 • Change from baseline (Day 84) in Clinic Visit trough FEV₁ measured pre- and post-bronchodilator at Day 112, 140 and 168 • Rate of moderate and severe COPD exacerbation(s) during the 12-Week Follow-Up Period • Rate of moderate and severe COPD exacerbation(s) over the 24-week study duration • Time to next exacerbation following cessation of double blind study treatment • Proportion of responders using the CAT at Days 112 and 168 • Change from baseline (Day 1) in CAT Total score at Days 112 and 168 • Proportion of responders on the SGRQ Total Score as measured by the SGRQ-C at Days 112 and 168 • Change from baseline (Day 1) in SGRQ total score at Days 112 and 168 • Severity of subsequent HCRU exacerbation defined by EXACT • E-RS: COPD and subscales from last dose of double-blind study treatment • Rescue medication use up to Day 112

